#### 12.4.1. Assessment of Adverse Event Intensity

When the determination of AE intensity rests on medical judgment, the determination of intensity must be made with the appropriate involvement of the investigator or a qualified sub-investigator.

The definitions/classification for rating intensity will follow the guidelines outlined in CTCAE version 4.0 (published 28 May 2009), which includes:

• Grade 1 Mild; asymptomatic or mild symptoms; clinical or diagnostic observations only; intervention not indicated

- Grade 2 Moderate; minimal, local, or noninvasive intervention indicated; limiting age-appropriate instrumental activities of daily living
- **Grade 3** Severe or medically significant but not immediately life-threatening; hospitalization or prolongation of hospitalization indicated; disabling; limiting self-care activities of daily living
- Grade 4 Life-threatening consequences; urgent intervention indicated
- Grade 5 Death related to AE

Note: A semi-colon indicates 'or' within the description of the grade.

Note: Instrumental activities of daily living refer to preparing meals, shopping for groceries or clothes, using the telephone, managing money, etc.

Note: Self-care activities of daily living refer to bathing, dressing and undressing, feeding self, using the toilet, taking medications, and not bedridden.

#### 12.4.2. Distinction Between Serious and Severe Adverse Events

It is important to distinguish between SAEs and AEs that are severe (Grade 3 or greater). Severity is a measure of intensity whereas seriousness is defined by the criteria under Section 12.2.1.2. An AE of severe intensity may not be considered serious. Adverse events of severe intensity are not SAEs unless any of the listed outcomes in Section 12.2.1.2 occurs. Adverse events of any intensity must be reported as SAEs if at least any of the listed outcomes in Section 12.2.1.2 occurs.

#### 12.4.3. Changes in Laboratory Values, Blood Pressure, or Other Measures

Consistent with Section 12.2.1.1, out-of-normal range results for laboratory values, blood pressure, and other measures (eg, pulse) are not required to be reported as AEs. Only results that the investigator deems clinically significant are to be reported as an AE or SAE.

# 12.5. Reporting Adverse Events

The COVID-19 contingency measures (see Remote Patient Visit Plan) do not affect the reporting timelines for AEs and SAEs described below in Section 12.5.1, Section 12.5.2, and Section 12.5.3.

## 12.5.1. Reporting of Adverse Events

The clinical course of each AE is to be followed according to accepted standards of medical practice.

In the case of withdrawal due to an AE or SAE, the subject is to be followed until resolution of the event, or until (in the opinion of the investigator) the AE has stabilized and the investigator does not expect any further improvement or worsening of the subject's condition and/or the subject has been referred to their primary physician for appropriate management of the ongoing event. Relevant clinical assessments and laboratory tests are to be repeated as clinically appropriate, such as until final resolution or stabilization of the event(s). Reasonable efforts are

to be made to contact any subject who fails to attend any follow-up appointments in order to ensure that he/she is in satisfactory health.

If the investigator considers it necessary to report an AE in a study subject more than 30 days after their last visit, he or she is instructed to contact Amicus to determine how the AE must be documented and reported.

Investigators are also responsible for reporting AE information to the relevant IRB in accordance with the requirements of their institutions.

#### 12.5.2. Reporting of Serious Adverse Events

All SAEs are to be documented and reported to Amicus immediately, but no later than 24 hours of any study personnel knowledge of events, regardless of any assessment of the event as related or not related to study treatment. Each SAE report is to be faxed to the designated safety fax number (+ 1 [contact]) to ensure appropriate dissemination and processing of the information. An alternate email address is provided as a backup (Table 1), if the fax transmission is unsuccessful.

If multiple SAEs are identified in a subject simultaneously, separate SAE reports are to be completed for each event.

The SAE forms, which will be provided by Amicus, are to be as complete as possible, with all known information at the time included. Reporting timelines (as described above) are not to be delayed while obtaining or preparing supporting information. All known details of the SAE, including an assessment of the causal relationship between the event and AT-GTX-501, are to be included in the initial report. All available relevant supporting documentation (eg, admission and progress notes, results of diagnostic evaluations/procedures/examinations, etc) available at the time of initial reporting are also to be included. All supporting documents are to be thoroughly reviewed and de-identified in accordance with local data privacy regulations prior to sending to Amicus. If submitted by fax, the subject's study number must be included in the subject line of the email.

Information not available at the time of the initial report (eg, event end date and outcome, discharge summary, etc) must be faxed to the designated safety fax number within 24 hours of any study personnel knowledge of the information (or emailed if the fax is unsuccessful). As when included in initial reports, all supporting documents are to be thoroughly reviewed and de-identified in accordance with local data privacy regulations prior to submission to Amicus. If submitted by fax, the subject's study number must be included on each page included in the fax. If submitted by email, the subject's study number must be included in the subject line of the email.

For any AE resulting in death, any available autopsy/pathologist's report is to be supplied.

Concomitant medications, AE, or other information obtained through SAE reporting must also be recorded in the appropriate CRF. If new medical or medication history is obtained via SAE reporting, the addition of the data to the clinical database is to be reported in an appropriate CRF.

If the investigator becomes aware of an SAE in a subject or receives an unsolicited report of an SAE from a subject more than 30 days after their last study visit and considers the event

possibly, probably, or definitely related to previously receiving AT-GTX-501, they are instructed to contact Amicus to determine how the SAE is to be documented and reported.

#### 12.5.3. Additional Reporting Requirements for Suspected Unexpected Serious Adverse Reactions

Any AE that is serious, unexpected, and associated with the use of study treatment has additional reporting requirements. For each SAE, Amicus will determine the expectedness of AEs according to current safety reference document.

Amicus is responsible for processing suspected unexpected serious adverse reactions (SUSARs). These SUSAR reports are also referred to as alert reports, expedited safety reports, and investigational new drug (IND) safety reports. A SUSAR is defined as any SAE that is determined to be associated with the use of the study treatment and is unexpected (not currently listed in the current safety reference document, as described in Section 12.2.1.3, or is not listed at the specificity or severity that has been observed).

Amicus will ensure SUSARs are reported to the FDA, in accordance with local laws.

- If the SUSAR is fatal or life-threatening, regulatory authorities and ethics committees are to be notified within 7 calendar days after Amicus learns of the event.
- If the SUSAR is not fatal or life-threatening, regulatory authorities and ethics committees are to be notified within 15 calendar days after Amicus learns of the event.

Additionally, safety updates will be provided periodically to the FDA and the relevant IRB. These updates will include information on SUSARs as well as other relevant safety findings.

# **12.6.** Other Reporting Situations

## 12.6.1. Reporting Information from Subject's Primary Care Physician

Throughout the study, any routine or non-routine visits to a subject's primary care physician, or other medical care received during the study, are to be reported to study personnel. Informed consent will include consent to collect any relevant medical records from the subject's other medical care providers. Also, close communication will be established by the investigator or their delegate with the primary care physician for each subject and will be maintained throughout the study. For the primary care physician, the important hallmarks of the study along with the proposed reporting plan will be explained. Laboratory reports, hospitalizations, clinical notes, and any other relevant medical records will be requested at the time of their occurrence.

As appropriate, the investigator or their delegate will report salient information received on the appropriate CRF (eg, AEs and concomitant medications).

# 13. STATISTICS

An overview of known statistical considerations is included below. Descriptions of all endpoints and their planned analyses will be detailed in the Statistical Analysis Plan (SAP).

## 13.1. Endpoints

## 13.1.1. Safety Endpoints

The safety endpoints will be defined based on parameters from the assessments described within Section 12.

#### **13.1.2.** Efficacy Endpoints

The efficacy endpoints will be defined based on parameters from the assessments described within Section 11. The primary efficacy outcome will be based on the Hamburg Motor and Language scores.

# **13.2.** Statistical Methods

#### **13.2.1.** General Considerations

As appropriate, data analyses will be analyzed both with respect to the subject's age and respective date of receipt of AT-GTX-501. If a subject has 1 or more siblings who was untreated and for whom relevant data are available, or a sibling who was also treated with AT-GTX-501, relevant comparisons will be presented. If needed, separate analyses will be performed for subjects who receive other treatments that may be disease-altering (eg, another approach to gene transfer or other investigative or prescription product). Natural history data on patients with vLINCL6 disease and/or pre-treatment data from subjects in Study AT-GTX-501-01 may also be included in analyses. As needed and as possible, analyses will account for changes in assessment methodology, such as a change in the cognitive assessment as per the study neuropsychologist (see Section 11.6).

By-subject listings will be prepared for all eCRF-collected data.

## **13.2.1.1.** Baseline Definition

Baseline is generally defined as the measure immediately preceding receipt of AT-GTX-501.

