### 8.2. Subject Exclusion Criteria

- 1. Presence of another inherited neurologic disease, eg, other forms of Batten disease (also known as NCL) or seizures unrelated to vLINCL6 disease (Subjects with febrile seizures may be eligible at discretion of the investigator.)
- 2. Presence of another neurological illness that may have caused cognitive decline (eg, trauma, meningitis, hemorrhage) before screening
- 3. Active viral infection (includes HIV or serology positive for hepatitis B or C)
- 4. Has received stem cell or bone marrow transplantation for vLINCL6 disease
- 5. Contraindications for intrathecal administration of the product or lumbar puncture, such as bleeding disorders or other medical conditions (eg, spina bifida, meningitis, or clotting abnormalities)
- 6. Contraindications for magnetic resonance imaging (MRI) scans (eg, cardiac pacemaker, metal fragment or chip in the eye, aneurysm clip in the brain)
- 7. Episode of generalized motor status epilepticus within 4 weeks before the gene transfer visit (Visit 2)
- 8. Severe infection (eg, pneumonia, pyelonephritis, or meningitis) within 4 weeks before the gene transfer visit (Visit 2) (Enrollment may be postponed.)
- 9. Has received any investigational medication within 30 days before the gene transfer visit (Visit 2)
- 10. Anti-AAV9 antibody titers > 1:50 as determined by ELISA (enzyme-linked immunosorbent assay)
- 11. Has a medical condition or extenuating circumstance that, in the opinion of the investigator, might compromise the subject's ability to comply with the protocol-required testing or procedures or compromise the subject's wellbeing, safety, or clinical interpretability

- 12. Pregnancy any time during the study (Any female subject judged by the investigator to be of childbearing potential will be tested for pregnancy.)
- 13. Abnormal laboratory values from screening considered clinically significant (gamma-glutamyl transferase [GGT] > 3 times the upper limit of normal, bilirubin ≥ 3.0 mg/dL, creatinine ≥ 1.8 mg/dL, hemoglobin < 8 or > 18 g/dL, white blood cells > 15,000 per cmm)
- 14. Family does not want to disclose subject's study participation with primary care physician and other medical providers.
- 15. History of or current chemotherapy, radiotherapy, or other immunosuppression therapy within the 30 days preceding screening (Corticosteroid treatment may be permitted at the discretion of the investigator.)

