#### 9.1.1. Prophylactic Administration of Prednisolone/Prednisone

Subjects will be started on an oral dose of prophylactic prednisolone/prednisone (glucocorticoid) 1 day prior to gene transfer via AT-GTX-501. In most cases this will be prednisolone, 1 mg/kg/day with a maximum dose of 60 mg/day. Prednisone at the same dose is acceptable as well as a comparable glucocorticoid administered intravenously if it were to be required. The glucocorticoid is intended to serve as an immunosuppressive to dampen host immune response to AAV or transgene, which is an expected reaction following gene transfer.

Oral prednisone or prednisolone administration will continue after the gene transfer itself and will be tapered according to results from measuring AST, ALT, GGT, and bilirubin (total and fractionated [direct and indirect]) to assess liver function and from interferon gamma (IFN- $\gamma$ ) T-cell studies (enzyme-linked immunospot [ELISpot] assays) to assess immune response to AAV9 and CLN6 peptides in the following weeks.

- Post-gene transfer, at some time after Day 30, the subject's prednisone or prednisolone dose may begin to be tapered if (1) AST, ALT, GGT, and bilirubin results while on-steroid are not considered clinically significantly abnormal by the investigator, and if (2) ELISpot responses to both AAV9 and CLN6 peptides are negative or mildly positive per laboratory criteria. Tapering will proceed slowly, typically over 4 to 7 weeks.
  - Depending on the discretion of the investigator, the steroid dose may instead be increased (eg, to approximately 2 mg/kg/day). Accordingly, the subsequent tapering protocol would be prolonged; however, the guidelines for tapering as described above will be followed.
- At any point, if either the AST or ALT exceed > 2.5X the subject's Visit 1 (screening/baseline) values, and results are confirmed on a follow-up blood test within 3 days, the prednisone or prednisolone regimen will be maintained or increased (at the investigator's discretion) until the enzyme levels fall below the 2.5X elevation.

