Based upon other studies, it is anticipated that oral prednisone or prednisolone administration will not exceed 120 days post gene transfer; regardless, testing of AST, ALT, GGT, and bilirubin is included at every site visit (at Days 7, 14, 21, and 30, at Months 3, 6, 9, and 12, and then every 6 months through Month 24). Additional assessments of AST, ALT, GGT, and bilirubin will be performed as needed; at a minimum these parameters will be measured and evaluated 1 to 2 weeks before initiating the planned final dose of steroid (ie, when tapering is almost complete) and 2 weeks after the final dose of steroid. During the period of COVID-19 contingency

measures, the sample collection and measurement of AST, ALT, GGT, and bilirubin may be performed locally rather than at the study site (see Remote Patient Visit Plan).

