WINCI ( diagan	Screening	Gen	e Trans	fer (Vi	sit 2)	Visit 3	Visit 4	Visit 5	Visit 6	Visit 7	Visit 8 a	Visit 9ª	Visit 10 a	Visit 11 a	Visit 12ª	Visit 13ª	Visit 14 a
vLINCL6 disease Study Procedures	Day -30 to -2	Day -1	Day 0	Day 1	Day 2	Day 7	Day 14	Day 21	Day 30	Mont h 3	Month 6	Month 9	Month 12	Month 15	Month 18	Month 21	Month 24
Visit window						±2d	±2d	±2d	±2d	±30d	±30d	±30d	±30d	±30d	±30d	±30d	±30d
Infusion site photographs (Section 9.1.2, Section 12.1.3)	Х	Х	Х	Х	Х	Х	Х	Х	Х								
Hamburg with video and UBDRS (Section 11.1, Section 11.2)	Х								Х	Х	Х	Х	Х	Х	Х	Х	Х
Long-term monitoring EEG (Section 11.4)	X												Х				Х
Ophthalmologic exams (Section 11.7)	Х								Х		Х		Х		Х		Х
Cognitive and language evals (Section 11.6)	X										Х		Х				Х
Electrocardiogram (Section 12.1.4)	Х												Х				Х
Safety labs (blood and urine) Section 12.1.5.1)	X	Х	Х	Х	Х	Х	Х	Х	Х	Х	Х	Х	Х	Х	Х	Х	Х
Additional assessments of AST, ALT, GGT, and Bilirubin (Section 12.1.5.1)			As needed as per Section 9.1.1. At a minimum these will be measured and evaluated 1 to 2 weeks before initiating the final dose of steroid (during down-tapering) and 2 weeks after the last dose of steroid. If necessary, these may be performed locally.														
HIV and Hep B or C (Section 12.1.5.1)	Х																

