## 12.1.5.1. Clinical Safety Laboratory Assessments

Samples collected for clinical safety laboratory assessments, including serum chemistry, hematology, and urinalysis (Table 4) will be performed prior to injection from Day -30 to Day -2 (baseline), Visit 2, and at follow-up visits. During the period of time in which COVID-19 contingency measures are in place, the subject may have samples collected at a local laboratory

for the clinical safety laboratory assessments (see Remote Patient Visit Plan). For subjects who utilize local laboratory sample collection, local laboratory normal ranges are to be reported. Subject's fasting status is to be recorded. For baseline on Day -1 and all post-transfer days except Day 21, prothrombin time (PT), international normalized ratio (INR), activated partial thromboplastin time (APTT), and fibrinogen will be measured. These may also be performed at additional time points at the investigator's discretion. At Visit 1, subjects will also be evaluated to ensure there is no active viral infection (includes HIV or serology positive for hepatitis B or C). Repeat or further blood or urine testing (eg, blood smear and urine microscopy) may be done for abnormal values at the investigator's discretion (reflex testing).

The clinical safety laboratory assessments include ALT, AST, GGT, and bilirubin. These analytes will also be tested as needed, including 1 to 2 weeks before initiating the final dose of steroid (during down-tapering) and 2 weeks after the final dose of steroid (see Section 9.1.1). As needed, these assessments may be performed locally.

Serum Chemistry	Hematology	Urinalysis

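### For hematology, the general baseline rule selects a sample on or after the day prophylactic steroid starts, while Section 12.1.5.1 labels Day -30 to Day -2 as baseline for the same tests

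*Protocol*

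**What the plan says.** Protocol Section 13.2.1.1, repeated in the synopsis under Statistical Methods, gives one general rule: "Baseline is generally defined as the measure immediately preceding receipt of AT-GTX-501".

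Section 12.1.5.1 says that serum chemistry, hematology and urinalysis "will be performed prior to injection from Day -30 to Day -2 (baseline), Visit 2, and at follow-up visits". The baseline label sits on the screening window, and Visit 2 (Day -1 to Day 2) is listed separately. For coagulation tests, the same section places baseline on Day -1.

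In Table 3 (Section 9.5.1), the row that begins "Safety labs (blood and urine" is marked at screening, Day -1, Day 0 and every later visit.

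Section 9.1.1 sets the steroid timing: "Subjects will be started on an oral dose of prophylactic prednisolone/prednisone (glucocorticoid) 1 day prior to gene transfer via AT-GTX-501". It adds that "at some time after Day 30, the subject's prednisone or prednisolone dose may begin to be tapered", subject to laboratory conditions, and that "it is anticipated that oral prednisone or prednisolone administration will not exceed 120 days post gene transfer".

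Section 12.2.1.4 expects neutrophils, and with them leukocytes, to rise by up to 5000 cells/mm3 over the subject's baseline value within 5 hours of starting steroid. It attributes the figure to studies in healthy adult volunteers and does not date the baseline value.

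Section 13.2.4.2 promises descriptive statistics for laboratory data by visit, and for change from baseline at each post-baseline visit.

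**The concern.** The study has no control arm, so in a change-from-baseline table each subject's own baseline is the only reference. The protocol itself predicts that steroid moves neutrophil and leukocyte counts within hours. Its general rule nevertheless picks a sample from the day steroid starts or the day after, while the section that schedules the tests puts the baseline label on an earlier window.

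If the steroid rise is already in the baseline count, two things follow. During steroid treatment the summaries understate the rise. After taper, a subject who has only returned to the pre-steroid level appears to have lost cells. In a first-in-human gene transfer study with about 13 subjects, a late fall in neutrophils or leukocytes is something a safety reader would try to explain.

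**Working it through.** **Which sample the general rule selects.** The candidates are the Table 3 safety-lab days up to gene transfer: screening (Day -30 to -2), Day -1 and Day 0.

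| Day 0 sample drawn | Last sample before injection | Within Day -30 to -2? | On or after steroid start day (Day -1)? |
|---|---|---|---|
| before injection | Day 0 | no | yes, the day after |
| after injection | Day -1 | no | yes, the same day |

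In both cases the selected day differs from the window labelled baseline in Section 12.1.5.1. The two candidate baselines lie from 1 day (Day -2 to Day -1) to 30 days (Day -30 to Day 0) apart.

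**Size of the offset.** Let P be the pre-steroid count, s the steroid rise already present in the selected sample, and Y the count at a later visit.

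- Change from the pre-steroid value: Y - P
- Change from the selected sample: Y - (P + s) = (Y - P) - s

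The two differ by -s. Section 12.2.1.4 bounds s at 0 to 5000 cells/mm3. With r the true rise over P at an on-steroid visit:

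| s (cells/mm3) | On-steroid change shown instead of r | Change shown after return to P (true value 0) |
|---|---|---|
| 0 | r | 0 |
| 2500 | r - 2500 | -2500 |
| 5000 | r - 5000 | -5000 |

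The middle row is for illustration. The protocol gives no value for these children about a day after the first dose. If the selected sample is a Day -1 draw taken before that dose, s = 0.

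**Which visits are on and off steroid.** Table 3 has 14 post-transfer safety-lab points, counting a month as 30 days:

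- Days 1, 2, 7, 14, 21 and 30: 6 points on steroid, since taper begins only after Day 30.
- Month 3: 1 point, window Day 60 to 120 (90 ± 30), mixed.
- Months 6, 9, 12, 15, 18, 21 and 24: 7 points. The earliest Month 6 visit is Day 180 - 30 = 150, which is past Day 120, so these are off steroid if the anticipated limit holds.

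Half of the scheduled points would therefore compare an off-steroid count with a reference that may be on steroid.

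**The case against.** The case on the other side is substantial, and most of it stands.

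- **The label may be only a visit name.** Day -30 to Day -2 is called baseline, or baseline/screening, throughout Sections 11 and 12. A reader might infer two competing analysis rules. The documents do not establish that: Section 12 schedules assessments and Section 13 governs the analysis. Against this, Section 12.1.5.1 uses the word for Day -1 when it turns to coagulation, so it is not a uniform visit name there.
- **The word 'generally' permits exceptions**, and the SAP may set a laboratory-specific baseline. That is true. The remaining point is that the protocol's rule, applied as written, gives an unsuitable reference for the off-steroid visits.
- **The baseline may not be on steroid at all.** A reader might infer that it certainly is. The order of the Day -1 draw and the first dose is not stated. Section 12.1.2 asks for start and stop dates of medications, which does not show that times go unrecorded elsewhere.
- **The last value before injection is a legitimate reference for the test product.** For visits up to Day 30 it isolates the vector effect better than a pre-steroid value. Section 12.2.1.4 anticipates an early leukocyte decrease, which a pre-steroid reference could mask behind the steroid rise. This stands, and it is why that change should be kept for on-steroid visits.
- **The rise in Section 12.2.1.4 is understood from context as relative to a pre-steroid value.** Agreed. That supports naming such a value as the reference.

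**Conclusion.** The point holds as a limited defect in the baseline rule for hematology. As written, the rule can set off-steroid counts, from about Month 6 onward, against an on-steroid reference. The offset is bounded by the protocol's own healthy-adult figure and has a floor of zero; its actual size in these children is unknown.

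The conclusion assumes that Table 3 is followed, that steroid starts on Day -1, that it ends within the anticipated 120 days, and that counts return to the pre-steroid level afterwards. It also takes Visit 1 as free of steroid. That may not hold for every subject, because exclusion criterion 15 adds: "Corticosteroid treatment may be permitted at the discretion of the investigator".

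The effect is confined to descriptive change summaries for neutrophils and leukocytes. A reader might infer that the anticipated-rise limit moves with the baseline and so changes which events count as dose-limiting. The documents do not support this: Section 12.2.1.5 defines a DLT by relatedness, CTCAE grade and being unanticipated, and refers to no baseline value. Efficacy is not touched. The AST/ALT trigger in Section 9.1.1 names Visit 1 and works as written, and the Day -1 coagulation baseline agrees with the general rule. By-visit values and listings remain correct. For chemistry and urinalysis the labels differ in the same way, but no consequence has been shown. Priority is low.

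**What to change.** Reconcile Sections 12.1.5.1, 12.2.1.4 and 13.2.1.1:

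1. State that the reference for hematology change from baseline is the last value before the first prophylactic steroid dose. This is Visit 1, or Day -1 where that sample is documented as pre-dose.
2. For on-steroid visits, also present change from the last pre-injection value, so that an early leukocyte decrease is not hidden by the steroid rise.
3. State that the baseline value in Section 12.2.1.4 is the pre-steroid value.
4. For chemistry and urinalysis, state whether the label in Section 12.1.5.1 is a visit name or the analysis baseline.

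The coagulation baseline and every steroid-management rule stay as they are.

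The cost is wording plus one extra change column; all samples are already scheduled. The main drawback is that the pre-steroid reference may be up to about 30 days before dosing.
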